Improving Patient Comfort of Vibratory Anesthetic Devices with a Cotton Dampener

01/29/2025

NCT06916468

Objectives

The study aims to determine the effectiveness of cotton as a dampener for vibratory anesthetic devices (VADs) for dermatologic patients. It will compare patient preferences for VAD use with and without cotton across different anatomical sites and identify factors, such as chronic pain or neuropathy status, that may influence these preferences. Finally, the study seeks to generate preliminary data to inform potential modifications to VAD use, optimizing patient comfort in dermatologic procedures.

Background

Vibratory anesthetic devices (VADs) decrease pain associated with anesthetic, steroid, or botulinum toxin injection in dermatology patients through the application of vibratory stimulation on targeted anatomical site [1,2,3]. While VADs are effective at reducing injection pain, a number of factors influence their adoption by injectors. One factor is patient comfort [4]. Anecdotally, some patients have reported discomfort with VADs used before dermatologic procedures. As this may be influencing the utilization of VADs in dermatological procedures, further investigation into patient comfort with VAD is necessary. This study will determine whether utilizing cotton balls as a dampener is effective in improving patient comfort with VAD use.

Inclusion and Exclusion Criteria

The study will include potential participants based on their ability to provide informed consent and complete the study, while excluding those with skin conditions, sensitivities at testing sites, or allergies to nitrile gloves or cotton.

Inclusion Criteria	
1.	Age range: from 18+
2.	Dermatologic patients at Westlake Clinic
3.	Consent: Must provide informed consent to participate in the study.
4.	Availability: Able to complete the entire study session, which includes testing all sites in a single session

Exclusion Criteria	
1.	Broken skin or known peripheral neuropathy on anatomical site of vibration.
2.	Allergies: Known allergy or sensitivity to nitrile gloves or cotton
3.	
4.	

Study Design

The overall study design is a single-site, one-visit, participant-blinded, pilot study for up to 60 patients in the Westlake dermatology clinic.

Study Procedures

The study is a single-site, participant-blinded, pilot study for up to 60 patients in the Westlake dermatology clinic. Using the pen-like VAD, vibration will be applied with cotton on an anatomical site of one side (right or left) and without cotton on the same anatomical site on the other side. To fix cotton to the VAD, a cotton ball will be positioned at the tip of the VAD with placement into a nitrile glove (5). The VAD we are using for this procedure is the current standard of care and is not a novel device.

The anatomical sites were chosen in terms of sites with minimal subcutaneous fat and areas where patients have anecdotally reported discomfort with the VAD. The sites will be the lateral nasal wall, sub-malar region of the cheek, ear helix, lateral neck, and dorsal side of the forearm.

The order of the five anatomical sites and the order of conditions (VAD and VAD with cotton) will be randomized, and all possible orders will be placed into an envelope. One envelope will be randomly selected for each patient to determine the order of anatomical sites and order of condition for that particular patient. The patients will be blinded to what treatment is applied. For example, patients will be instructed to close their eyes or to look away from the application site.

There will be 10 total applications (VAD and VAD with cotton for five anatomical sites) each subject will undergo. Each application of the VAD will last for 20 seconds. Between each VAD application, there will be a delay of 10 seconds. After applying vibration to the same anatomical sites on the left and right side, patients will be asked which of the two treatments was preferred, which should take around one minute. To monitor participants for safety, participants will be encouraged to report any discomfort or adverse effects they experience during or after each vibration and after each VAD application, participants will be asked if they are ready to move on to the next one.

Before completion of the protocol, but after the informed consent, patients will be asked questions regarding their medical history. Additionally, before administering vibrations, patients will be trained to distinguish between small and large dowels, applying the minimum amount of pressure, while their eyes are closed to ensure accurate perception of the vibration.

Data will be patient reported and will be collected in a secure RedCap online database.

Study Timeline

Estimated time requirement of visit	Visit 1
Patient Screening and Informed Consent	10 minutes
Data Collection	15 minutes
Anatomical site vibration (10)	15 minutes

Data to be Collected for your study

The study will collect sociodemographic information, including age, gender, and race, to understand the generalizability of data. Medical history data will encompass past medical conditions, history of prior procedures, and any previous use of vibration before injection. Patient chart will be looked at for the purpose of validating patient survey questions. Chronic pain history will be recorded, including the participant's relationship with a chronic pain specialist, current use and duration of pain medication, the specific medication used, and the

type, location, and duration of chronic pain. The presence, history, and location of neuropathy will also be documented. Lastly, the primary outcome variable will assess participant preference for each anatomical site, comparing the use of cotton versus no cotton.

Data Analysis Plan

As this is a pilot study, we are not able to conduct a power analysis. However, similar studies at UH using this same VAD have a similar target of up to 60 patients. A binomial test will be used to determine whether the proportion of participants preferring cotton differs significantly from the expected 50/50 baseline for each anatomical site. Additionally, Chi-Square Tests of Independence will be conducted to assess whether preferences for cotton versus no cotton vary based on participant characteristics, including chronic pain status, neuropathy status, or anatomical site. Qualitative data on the reason behind preference will be asked and independently categorized by at least two raters.

Risks to Research Participants

Minor discomfort may be experienced by patients from vibration for a few seconds per site. Additionally, there might be an anxiety due to potential discomfort. There will also be a risk of breach of confidentiality. Participants will be informed that they can withdraw from the study at any time without penalty.

Provisions to Protect the Privacy Interests of Research Participants

Vibration tests will occur in private rooms. All collected data will be de-identified in RedCap, ensuring that no personally identifiable information is linked to study responses. Data will be securely stored in a password-protected, restricted-access database of REDCap, with access limited to authorized research personnel only. A coding system will be used, where a unique participant code is linked to each subject's data. Only authorized research personnel will have access to this code, and it will be securely stored separately from the study data in a linking log.

Potential Benefit to Research Participants

There is no direct benefit to research participants. Indirectly, if the use of cotton with vibration proves to be more comfortable for patients, it could provide a simple, cost-effective, and widely implementable solution for VAD use which optimizes patient comfort. This could be especially

beneficial for individuals with heightened pain sensitivity, such as those with chronic pain or neuropathy.

Withdrawal of Research Participants

Participants will be withdrawn from the study if they experience unexpected or intolerable discomfort that prevents them from completing the procedure. Additionally, participants may be withdrawn if they do not follow study instructions properly, which could compromise the integrity of the data collection process. If a participant withdraws before completing the procedure, their data will not be included in the study analysis. If a participant is withdrawn due to noncompliance or intolerable discomfort, their collected data will be discarded. Participants will be informed of their right to withdraw at any time without penalty.

Alternatives to Participation

The alternative to participation is not to participate.

Drugs or Devices

The pen-like vibratory anesthetic device which is the current standard of care in UH dermatology clinics and is not a novel device will be the main device used for this study on 5 anatomical sites each on the left and right side.

Additional Information

This VAD used is a current standard of care for dermatologic procedures, and this is not a novel device.

Community-Based Participatory Research

This is not community-based participatory research.

References

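### Does excluding known neuropathy at the tested sites undermine the planned comparison by neuropathy status?

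*Combined protocol and SAP*

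**What the plan says.** - **Exclusion Criteria, item 1:** "Broken skin or known peripheral neuropathy on anatomical site of vibration".
- **Inclusion Criteria, item 4:** a participant must be "Able to complete the entire study session, which includes testing all sites in a single session".
- **Study Procedures:** "The sites will be the lateral nasal wall, sub-malar region of the cheek, ear helix, lateral neck, and dorsal side of the forearm". Also: "There will be 10 total applications (VAD and VAD with cotton for five anatomical sites) each subject will undergo".
- **Withdrawal of Research Participants:** data from anyone who withdraws before finishing are left out of the analysis.
- **Objectives:** the study will "identify factors, such as chronic pain or neuropathy status, that may influence these preferences".
- **Data to be Collected:** "The presence, history, and location of neuropathy will also be documented".
- **Data Analysis Plan:** chi-square tests of independence will relate preference to participant characteristics, "including chronic pain status, neuropathy status, or anatomical site". Neuropathy status is not defined there or elsewhere.
- **Potential Benefit to Research Participants:** if cotton proves more comfortable, it could be especially "beneficial for individuals with heightened pain sensitivity, such as those with chronic pain or neuropathy".

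**The concern.** Eligibility and analysis seem to pull in different directions. The natural clinical question is whether a patient with altered sensation where the device is applied feels the dampener differently. The exclusion removes the patients known to be in that position, while the objective and the chi-square test keep the unqualified term.

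Two things would be at stake. First, a result reported simply as an effect, or no effect, of neuropathy on preference would reach beyond the people enrolled, and the benefit statement names people with neuropathy in general. Second, because presence, history and location are all collected and none is named as the analysis variable, two analysts could code the factor differently.

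**Working it through.** The documents give no figure on this point: no neuropathy prevalence, subgroup size or power. The check is therefore mainly one of reading the sections together.

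**Step 1. Does the exclusion act on the person or on the site?** Read alone, it could mean that an affected site is skipped. Inclusion item 4, the ten applications per subject and the discarding of incomplete participants all point the other way. On that reading, known current neuropathy at any one of the five sites excludes the person.

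**Step 2. Who is left to compare?**

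| Neuropathy | Eligible? | Captured in the data? |
|---|---|---|
| Known and current, at a tested site | No (0 of up to 60 by rule) | Not applicable |
| Known, only outside the tested sites | Yes | Yes: presence and location |
| Past, at a tested site | Yes, if the exclusion means current disease | Yes: history and location |
| Undiagnosed, at a tested site | Yes | No; counted as none |
| None | Yes | Yes |

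The factor is not empty by design. The contrast is mainly neuropathy elsewhere against none.

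**Step 3. Is a comparison at the vibrated skin promised anywhere?** No. The Data Analysis Plan places neuropathy status beside chronic pain status as a characteristic of the participant. The Objectives use it in the same sense. The benefit sentence is conditional and speculative; it does not describe a test. None of these statements conflicts with the exclusion.

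**Step 4. Does any stated rule give a wrong answer?** No. The per-site binomial tests do not use neuropathy at all. The chi-square test by status can be run with the planned data, and its result applies to the people who were eligible. Writing the definition down would restate a limit that the exclusion already sets.

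**Step 5. Does the size of the subgroup change this?** The number with neuropathy is not given. As an assumption, take 3, 6 or 12 of 60 (5%, 10%, 20%), with two-thirds preferring cotton in both groups (40 of 60 overall, 20 not). For one site, the Newcombe 95% interval for the difference d = p1 − p2 = 0 uses the Wilson limits (l, u) of each group:

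- lower = d − √[(p1 − l1)² + (u2 − p2)²]
- upper = d + √[(u1 − p1)² + (p2 − l2)²]

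For 2/3 against 38/57 the Wilson limits are 0.208 to 0.939 and 0.537 to 0.775:

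- lower = −√(0.459² + 0.108²) = −0.472
- upper = √(0.272² + 0.130²) = 0.301

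The smallest expected cell is n × 20/60 for one site. If all five sites are pooled (300 answers, 100 of them not for cotton), it is 5n × 100/300.

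| n with neuropathy | Counts preferring cotton | 95% interval (points) | Smallest cell, one site | Smallest cell, five sites pooled |
|---|---|---|---|---|
| 3 | 2/3 vs 38/57 | −47 to +30 | 1 | 5 |
| 6 | 4/6 vs 36/54 | −38 to +27 | 2 | 10 |
| 12 | 8/12 vs 32/48 | −30 to +24 | 4 | 20 |

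The intervals are wide, but they measure the imprecision of a small subgroup, which would arise with or without the exclusion. They say nothing about how the variable is defined. The cell counts also turn on whether the test is run per site or pooled, which the plan does not say. Pooling would bring its own problem of repeated answers from one person, but that is a separate matter.

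**The case for a change.** The strongest case for a change is that identifying factors such as neuropathy is a stated objective, the variable is undefined, and the benefit section invites a general reading. Collecting location does not fix in advance how it will be used. A sentence or two settled before analysis would remove the freedom in coding and tie the conclusion to the people studied, with no new data and almost no cost.

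Part of this stands. The variable is undefined, and the result cannot speak to known neuropathy at the vibrated skin. A report should say so.

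The rest does not carry a change to the plan. The over-general conclusion is one that a future author might draw; the protocol draws none and describes its output as preliminary. Conclusions of any trial are bounded by its eligibility criteria, and plans do not usually repeat each boundary in the objectives and the analysis section. The obvious definition also needs care: counting only known neuropathy outside the five sites would leave past neuropathy at a tested site unclassified. An analyst with the presence, history and location fields can deal with that when coding. Advice to report the contrast descriptively because cells may be sparse answers a different question and rests on assumed subgroup sizes.

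**Conclusion.** The observation is accurate, but it describes missing detail rather than an error. Known neuropathy at a tested site is absent by rule (0 of up to 60), so the contrast mainly compares people with neuropathy elsewhere with people without it. That comparison is coherent, can be made with the data already planned, and has a limit visible in the eligibility criteria. The sections do not contradict one another, and no stated rule produces a wrong result.

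This rests on reading the exclusion at the level of the person, which inclusion item 4 and the ten applications per subject support, and on reading neuropathy status as a trait of the participant, as the Data Analysis Plan lists it. If the exclusion were meant site by site, the contrast would be broader and the concern weaker.

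Its reach is one secondary, exploratory test in a pilot with no power analysis. Analysts can be expected to define the variable from the recorded fields and to note in the report whom it covers. No change to the plan is needed.

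### Condition order comes from an unrestricted random draw, so cotton-first is balanced only in expectation, and the analysis takes no account of position

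*Combined protocol and SAP*

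**What the plan says.** Study Procedures states that "The order of the five anatomical sites and the order of conditions (VAD and VAD with cotton) will be randomized" and that "all possible orders will be placed into an envelope". The selection rule is: "One envelope will be randomly selected for each patient to determine the order of anatomical sites and order of condition for that particular patient". Each participant goes through five pairs: "There will be 10 total applications (VAD and VAD with cotton for five anatomical sites) each subject will undergo". The spacing is short: "Between each VAD application, there will be a delay of 10 seconds". The two members of a pair are applied to opposite sides of the body, and the participant then says which was preferred.

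The section does not say:
- whether an envelope holds one condition order for all five sites or a separate order for each site;
- whether a drawn envelope goes back into the pool;
- whether cotton-first is balanced, overall or by site.

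The Data Analysis Plan tests cotton preference at each site with a binomial test against 50/50. It adds chi-square tests by chronic pain, neuropathy and anatomical site. Neither uses the order of application, and the list of data to be collected does not include the sequence drawn. The size is given as a "pilot study for up to 60 patients in the Westlake dermatology clinic", without a power calculation.

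**The concern.** Each answer compares two short applications given one after the other, and the outcome is a subjective preference. Some participants may favour whichever application came first or second, whatever the tip. Randomising the order protects against this on average over hypothetical repeats of the trial. It does not protect the one sample obtained if cotton happens to come second much more often than first. In that sample a position habit adds to the apparent preference for cotton or hides a real one, and the plan provides neither an analysis nor a recorded variable that would show it.

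The number of orders per envelope also matters. If one condition order governs all five pairs, any chance imbalance recurs in the same direction at every site, and similar results across sites carry less independent information than they seem to. Comparison across anatomical sites is one of the stated objectives.

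**Working it through.** **Inputs from the documents.** Five sites and two conditions give 5 × 2 = 10 applications, which reproduces the plan's count. The maximum is 60 patients; this cannot be re-derived, since the plan says "As this is a pilot study, we are not able to conduct a power analysis". The test is a per-site binomial against 0.5.

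**Assumptions, not in the documents.** Two-sided alpha of 0.05; 60 completers; *q*, the probability of choosing the application in a given position when cotton has no effect, taken from 0.5 to 0.8; answers independent across sites given the order.

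**1. Size of the pool.** One condition order per patient: 5! × 2 = 120 × 2 = 240. One per site: 5! × 2⁵ = 120 × 32 = 3,840. Sixty draws exhaust neither, so completing the pool cannot produce balance.

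**2. Chance imbalance in cotton-first at a site.** Binomial(60, 0.5) for draws with replacement; hypergeometric(240, 120, 60) for draws without replacement from 240.
- Exactly 30/30: 10.3% with replacement, 11.8% without.
- 35/25 or worse: 24.5% with, 17.9% without (24.1% without replacement from 3,840).
- 38/22 or worse: 5.2% with, 2.5% without (5.0% from 3,840).
- Central 95% range of the cotton-first count: 22 to 38 with, 23 to 37 without (from 240).

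**3. Shift in the site estimate.** With no cotton effect and cotton in the favoured position for *k* of 60 patients, expected cotton preference is [*qk* + (1 − *q*)(60 − *k*)]/60.
- *k* = 38, *q* = 0.7: (26.6 + 6.6)/60 = 0.553. The mirror-image split gives 0.447.
- *k* = 38, *q* = 0.6: (22.8 + 8.8)/60 = 0.527.
- *k* = 30, any *q*: 0.500.

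**4. Type I error of the planned test.** At n = 60 the exact test rejects at 21 or fewer or 39 or more, an actual size of 0.0273.
- Averaged over draws with replacement it is 0.0273 for every *q* from 0.5 to 0.8. Without replacement from 240 it falls from 0.027 to 0.021.
- Conditional on a 38/22 split it is 0.037, 0.067 and 0.114 for *q* = 0.6, 0.7 and 0.8.
- With a forced 30/30 split it is 0.024, 0.016 and 0.006 for the same values, so the unadjusted test becomes conservative.

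**5. If one order is shared by all five sites.** The within-patient correlation between sites due to position is (2*q* − 1)², which is 0.16 at *q* = 0.7. The chance of two or more false positives in the same direction is 0.0083 at *q* = 0.7, against 0.0036 with separate orders per site. The chance of at least one does not rise (0.127 against 0.129). With separate random orders, only 2 × 0.5⁵ = 6.25% of patients would have the same direction at all five sites.

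**6. Precision at one site.** Suppose 30% of participants always choose by position and the rest choose at 50/50. With a random draw the standard error is √(0.25/60) = 6.5 points. With a forced 30/30 split, cotton is chosen with probability 0.35 in one position and 0.65 in the other, so it is √(0.35 × 0.65/60) = 6.2 points. With 10% answering by position it is √(0.45 × 0.55/60) = 6.4 points.

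**The case against.** The strongest reply is that order is already randomised in a small pilot, so the planned test is valid and only detail is missing. Much of this stands. The split is 30/30 in expectation, and no error rate of the per-site test is inflated on average. The 38/22 example is an edge case: the mean departure from 30/30 with replacement is about 3 patients (30 × 0.1026 = 3.1), a shift of about 2 points at *q* = 0.7 (3.1/60 × 0.4). The documents give no figure for a position effect, and applying the pair to opposite sides of the body weakens any local carry-over.

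A reader might infer that each envelope fixes one condition order for the whole session. The singular wording in "One envelope will be randomly selected for each patient to determine the order of anatomical sites and order of condition for that particular patient" allows this, but the plural in "The order of the five anatomical sites and the order of conditions (VAD and VAD with cotton) will be randomized" and the reference to all possible orders equally allow an order per site.

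A reader might also expect a large loss of precision. Over the pooled 300 answers, with 30% answering by position, the standard error is √(18 × 0.25 + 42 × 0.05)/60 = 4.3 points with one order per patient. It is √(18 × 0.01 + 42 × 0.05)/60 = 2.5 points when cotton is first at two or three sites. But the plan does not test a pooled proportion, and random order per site already gives √(0.25/300) = 2.9 points.

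What the reply does not answer is that balance is left to chance when it could be fixed in advance, and that the plan neither records nor reports position.

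**Conclusion.** The point holds as one of chance imbalance and interpretability. Cotton-first is balanced only in expectation, a split of 35/25 or worse has an 18% to 25% chance, and neither the analysis nor the data list deals with position. The consequence in an unlucky draw is a shift of about 5 points at 38/22 if 70% favour one position, and under 3 points if 60% do. Whether the five sites share that shift depends on a design detail that the text leaves open.

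The documents do not support the stronger inference that cotton is systematically tied to a position or that the binomial test is invalid: its average type I error stays at 0.027. All sizes rest on assumed position effects, 60 completers and a two-sided 0.05 level. The benefit of a change is real but modest, chiefly removal of chance position bias, with a per-site standard error of about 6.2 instead of 6.5 points if 30% answer by position.

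**What to change.** State whether condition order is set per patient or per site, and replace the open draw with a prepared set of sealed sequences in permuted blocks, each used once. Within each participant cotton comes first at two or three of the five sites; at each site it comes first in half of the sequences.

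Such a set exists. There are 10 patterns with cotton first at two sites and 10 with cotton first at three. Any given site is cotton-first in 4 of the former and 6 of the latter, hence 10 of 20, and three such sets make 60. Smaller blocks built from complementary pairs (each pattern with its reverse) keep the balance if enrolment stops early. Because the withdrawal rules discard data from non-completers, balance in the analysed set may be slightly off.

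Enter the sequence code in REDCap, and report cotton preference at each site separately for cotton-first and cotton-second participants. Balancing the order of the sites themselves, for example with a Latin square, is optional and not needed for this point.

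The cost is one list and envelope set, one database field and one table, with no added patients or visits. There are two small downsides. Operators follow a condition order that changes within the session. The unadjusted binomial test also becomes somewhat conservative if a position effect exists (0.016 against 0.027 at 70%).

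### Visual blinding is not assured at the lateral nasal wall, and possibly the cheek, because participants may look away instead of closing their eyes

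*Combined protocol and SAP*

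**What the plan says.** Under Study Design: "The overall study design is a single-site, one-visit, participant-blinded, pilot study for up to 60 patients". Study Procedures repeats the label and makes the commitment explicit: "The patients will be blinded to what treatment is applied". The next sentence gives the means, introduced as an example: "patients will be instructed to close their eyes or to look away from the application site".

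The same section lists where the device is applied: "The sites will be the lateral nasal wall, sub-malar region of the cheek, ear helix, lateral neck, and dorsal side of the forearm". It also describes how the conditions differ physically. For the cotton condition, "a cotton ball will be positioned at the tip of the VAD with placement into a nitrile glove". No glove is described for the device without cotton. On duration: "Each application of the VAD will last for 20 seconds".

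No eye cover, screen, site-specific masking rule or check of blinding appears anywhere in the document. Closed eyes are specified without an alternative only for the dowel training that precedes the vibrations.

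The section on data to be collected makes the participant's own preference at each site the primary outcome. The Data Analysis Plan tests that preference at each site against an even split with a binomial test, and uses chi-square tests to ask, among other things, whether preference varies by anatomical site.

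**The concern.** The participant is also the assessor, and the outcome is a subjective choice between two conditions. Participant blinding is therefore the main protection against a choice made on expectation. The two options in the masking instruction do not give equal protection. Closed eyes hide the device at any site. Looking away works for the forearm, because head and gaze can both turn from it. The side of the nose and the cheek turn with the head, so only the gaze can move away. A pen-like device held at the lateral nasal wall for 20 seconds is close to the eye and may remain in view. The case is weaker at the cheek.

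Two results are at stake. First, participants who see the padded tip may choose it because it looks softer, which would move the proportion at that site away from 50% with no difference in comfort. Second, sight of the tip would vary by site, being more likely at the nose than at the ear, neck or forearm. An apparent difference in preference between sites could then partly reflect how well each site was masked.

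**Working it through.** The plan gives no power, alpha, effect size or visibility figure on this point, so there is no stated number to reproduce. The check has two parts.

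**Reading the text**

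1. The label and the commitment are participant blinding, without exception by site.
2. The one instruction given joins closed eyes and looking away with 'or', and does not tie either to particular sites.
3. The conditions can be told apart by eye: a cotton ball in a glove at the tip, against a device for which no matching cover is described.
4. At least one site, the lateral nasal wall, is next to the eye and moves with the head. That looking away may fail there is an inference from anatomy; the document has no data on it.

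A session that follows the instruction exactly can therefore leave the tip visible to a participant at the nose.

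**What it could do to the test at one site**

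Inputs from the document: n = 60 (the maximum enrolment) and a null proportion of 0.5. Assumed, because the document gives no value: two-sided alpha of 0.05, an exact test, no true comfort difference, a share *u* of participants who see the tip, and a probability *q* that such a participant chooses cotton.

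Expected cotton preference: p = 0.5(1 − u) + q·u.

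- u = 0.20, q = 0.70: p = 0.40 + 0.14 = 0.54
- u = 0.50, q = 0.70: p = 0.25 + 0.35 = 0.60

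The exact test rejects when 39 or more, or 21 or fewer, of 60 prefer cotton. The chance of a significant result is P(X ≥ 39) + P(X ≤ 21), with X ~ Binomial(60, p):

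- p = 0.50 (nobody sees the tip): 2.7%
- p = 0.54: 5.8%
- p = 0.60: 25.7%

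The same calculation over a wider range of assumptions:

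| Share seeing the tip, u | q = 0.60 | q = 0.75 | q = 0.90 |
|---|---|---|---|
| 10% | 2.9% | 3.9% | 5.8% |
| 25% | 3.9% | 10.8% | 25.7% |
| 50% | 7.7% | 39.9% | 83.8% |

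The result runs from negligible to severe and depends wholly on *u* and *q*, neither of which is known.

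**The case against.** The strongest reply is that the same sentence also offers closed eyes, which hides the device at every site. Only participants who look away can be affected, and nothing says how many would. The sentence also opens as an example, so it need not be the full list of measures, and staff might sensibly use closed eyes for the face and looking away for the arm. All of this stands as a limit on the claim. It does not remove the gap, because the text does not make that allocation by site and an unstated further measure cannot be relied on.

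A reader might infer several stronger things that the document does not support:

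- *That participant blinding is not delivered at the facial sites.* This does not follow while closed eyes is one of the two options. What follows is that it is not assured.
- *That the device stays in view wherever the participant looks.* The document says nothing about device length, angle of approach or field of view.
- *That two sites of five, or 2 × 60 = 120 of 5 × 60 = 300 answers, are affected.* That would need full enrolment, would count participants with closed eyes, and would treat the cheek as fully equal to the nose.
- *That participants will see the tip changed in the 10-second delay.* The document does not say how or when tips are prepared, or whether one device serves both conditions. It is silent on masking in that interval, which is a missing detail and no evidence of unmasking.

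A further objection is that participants may feel the cotton even with eyes closed. That is fair, and it limits what the fix can achieve. But touch is part of what is being compared, whereas sight is an extra cue that can be avoided.

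**Conclusion.** The point holds in a limited form. As written, the plan does not assure visual blinding at the lateral nasal wall, and possibly the cheek, for participants who look away. The consequence is possible bias in the per-site preference and possible confounding of the comparison between sites.

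The size cannot be established from the document. The lower illustrative case, at 5.8%, barely exceeds a nominal 5%. The upper case, at 25.7%, needs half of the participants to look away and see the tip, with 70% of those choosing cotton. Both rest on assumed inputs, an assumed alpha and full enrolment of 60. The reason to act is that the better option is already in the sentence and costs little, and not that harm to the result has been shown.

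**What to change.** In Study Procedures, delete the option of looking away. Require eyes closed at all five sites, from before the device is brought to the first side until the preference for that pair has been given, including the delay between the two applications. State that the tips are kept out of the participant's sight.

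Cost: on the protocol's own timings, each pair takes 20 + 10 + 20 seconds plus about 60 seconds for the preference question, so about 110 seconds with eyes closed. Over five pairs that is 5 × 110 = 550 seconds, or about 9 minutes, inside the 15 minutes scheduled for the vibrations. Participants already close their eyes for the dowel training, so the instruction is familiar. Keeping the tips out of sight is a small extra step for staff. Sample size, visit and analysis do not change.

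The change removes the visual cue only. It does not mask the feel of a padded tip against a bare one, so the report should not claim more than visual masking on the strength of it.
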